## 14.5 Study Discontinuation

### 14.5.1 Subject Discontinuation

A subject can withdraw his/her consent for participation in the study at any time without prejudice. The Site Investigator may discontinue a subject if s/he deems it clinically appropriate for any reason. Additionally, the Site Investigator must discontinue a subject for any of the following reasons:

1. Cardiovascular events (see [Section 14.5.2](#)).
2. Serious medical problem thought to be related or unrelated to the study medications.
3. Intercurrent illness or medical complications that, in the opinion of the site investigator, preclude safe administration of study medications.
4. Evidence of illicit drug use while participating in the study during Days 1-7.
5. Alcohol or other sedative/hypnotic withdrawal signs and symptoms developing following enrollment into the study.
6. Requiring therapy with an exclusionary drug.
7. Lack of compliance with protocol and/or unit procedures.
8. During Days 1-7, missing more than 2 doses of study medication in a single 24-hour period or missing more than 6 doses of study medication prior to meeting “completer” criteria (i.e., receives at least one dose of study medication on Day 7 and completes the 3.5-hour post-dose SOWS-Gossop assessment on Day 7).

At any time after a subject meets “completer” criteria, they may be discontinued by the Investigator if s/he feels that the subject has achieved the treatment goal of acute detoxification/ transition. This judgment by the Site Investigator will be made and recorded daily in the subject’s source document and on the eCRF on Days 7 (after end of double-blind dosing but before initiating open label dosing) through 14.

Subjects who are removed from study treatment because of adverse events (AEs) or serious adverse (SAEs) will be followed until they are medically stabilized to the satisfaction of the attending physician (see [Sections 15.5.1](#), [16.7](#), and [16.8](#)). Appropriate safety evaluations will continue to be collected until the subject is discharged from the treatment center or the maximum 14-day treatment period has expired. This stabilization can include medically supervised opioid withdrawal (involving behavioral therapy, rescue opioid medications, and/or non-opioid pharmacotherapy) or referral to an appropriate methadone or buprenorphine therapy program.

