## 14.6 Concomitant Therapy

If the subject is admitted to the inpatient study unit the day before Baseline (i.e., Day -1), a single dose of a short-acting opioid (e.g., morphine) may be administered if needed to keep the subject reasonably comfortable; however, the administration may not occur after 8 PM on Day -1.

The concomitant medications or therapies listed below are permitted during Days 1-7 and Days 8-14 of the study.

1. Multivitamins ( $\leq 1$  tablet orally, administered daily at 9 AM).
2. Guaifenesin (for cough) ( $\leq 2$  teaspoons orally every 2 hours, as needed [PRN]).
3. Alumina, Magnesia, and Simethicone (for emesis and nausea) ( $\leq 30$  mL orally every 4 hours, PRN).
4. Dioctyl sodium sulfosuccinate (for constipation) ( $\leq 100$  mg orally every 8 hours, PRN).
5. Psyllium hydrocolloid suspension (for constipation) ( $\leq 1$  tablespoon orally every 12 hours, PRN).
6. Bismuth sulfate (Pepto-Bismol®) (for diarrhea) ( $\leq 6$  doses of 30 mL orally every 24 hours, PRN).
7. Acetaminophen (for headache, muscle aches, or other discomfort) ( $\leq 4$  doses of  $\leq 650$  mg orally every 24 hours).
8. Zolpidem (for insomnia) ( $\leq 10$  mg orally, PRN, may repeat 1 time if administered before 5:00 AM (i.e., 3 hours before the first morning dose of lofexidine or placebo). Zolpidem must not be administered before 11:00 PM (which is the time of the last daily dose of lofexidine or placebo).
  - 8a. Note: A short-acting benzodiazepine (e.g., oxazepam) may be used ad libitum for insomnia during the second part of the study (i.e., Days 8-14).
9. Nicotine replacement therapy (patch, inhaler, gum, nasal spray).

All other medications must be approved by the Sponsor's Medical Monitor before administration. If a subject requires any other medication for intolerable nausea and emesis (including a prescription opioid or non-opioid or an over-the-counter opioid or non-opioid) other than alumina, magnesia and simethicone, the subject will be discontinued from the study and given appropriate treatment according to the standard of care (see [Section 14.5.1](#)).

All medications taken will be recorded in the subject's source document and eCRF along with dose, dates of administration, and reason for use.

Psychosocial therapy (e.g., art, music, group sessions) will be allowed per standard of care at individual study sites. Acupuncture, however, will not be allowed. All therapies will be recorded in the subject's source document and eCRF.

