**Table 1. Schedule of Study Assessments**

Activity	Randomized, Double-Blind, Placebo-Controlled (Days 1-7) followed by Open-Label, Continuation Treatment (Days 8-14)				
	Screening	Baseline	Inpatient Treatment	In/Outpatient Treatment	Study Discontinuation/End of Study*
	Days -6 to -1	Day 1	Days 1-7	Days 8-14	
C-SSRS Baseline Version		X			
C-SSRS Since Last Visit Version			X (s)	X(t)	X
Urine Drug Screen (q)	X	X	X	X	X
Telephone Follow Up (h)					X

**Abbreviations:** BP = blood pressure; C-SSRS = Columbia Suicide Severity Scale; QID = 4 times daily

\* The study discontinuation/end of study assessments/procedures should always be done upon exit from the study.

- (a) The Baseline period is the morning of admission, before randomization.
- (b) This form is to be updated at Baseline.
- (c) A chest x-ray is required only if a PPD (purified protein derivative) skin test for tuberculosis is not done, the current PPD is positive, or if a past PPD was positive.
- (d) The urine sample collected on the first day of screening will be divided into two aliquots. One sample will be sent to the central lab ( ) for urinalysis and the other sample will be used for urine drug screening and immediate “dipstick” analysis of pregnancy (females only).
- (e) During Inpatient Treatment (Days 1-7), efficacy scales will be completed daily: the Short Opiate Withdrawal Scale of Gossop 3.5 hours (±10 minutes) after the first dose of study medication followed by the other efficacy scales shortly thereafter. Efficacy scales will be completed daily before dosing during Days 8-14.
- (f) The Objective Opiate Withdrawal Scale of Handelsman (OOWS-Handelsman) will be completed at Baseline to determine final eligibility as subjects must have a score ≥2 in order to participate in the study (inclusion criterion #4).
- (g) To be done at the end of double-blind dosing and before initiating open-label dosing.
- (h) The follow-up telephone contact will be 30 days after the subject’s last dose and will include an evaluation of the subject’s current treatment status (e.g., relapse, current psychosocial treatment, successful entry into a methadone, buprenorphine, or naltrexone program) and an adverse event evaluation.
- (i) Vital signs (resting [sitting/recumbent] and standing blood pressure and pulse; respiration, and temperature) will be measured before every dose and 3.5 hours after study medication administration at 8 AM, 1 PM, and 6 PM (7 times per day).

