### 15.3.3 Study Discontinuation/End of Study

Any subject that discontinues from the study, regardless of the reason (see all scenarios listed in [Section 14.5.1](#)), will be requested to complete all Study Discontinuation/End of Study assessments and procedures as listed below after the last dose of study medication:

- Concomitant medication assessment.
- Completion of detoxification as assessed by the Site Investigator.
- Pill count to measure compliance with previous day’s doses if not already performed.
- Blood pressure and pulse at rest (sitting or recumbent, if required, for treatment of an AE) and standing; respiration, and temperature.
- AE assessment.
- 12-lead ECGs (in duplicate).
- Clinical laboratory tests.
- Complete physical examination (including body weight).
- Pregnancy test.
- Urine drug screen.
- C-SSRS (Since Last Visit version; [Appendix 10](#)).
- SOWS-Gossop.
- OOWS-Handelsman.
- MCGI (Subject and Rater).
- VAS-E.
- COWS.

A 30-day post discharge follow-up telephone contact will be made 30 days after the subject’s last dose for an adverse event evaluation and an evaluation of the subject’s current treatment status (e.g., relapse, current psychosocial treatment, successful entry into a methadone, buprenorphine, or naltrexone program).

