The null hypothesis H_0 will be rejected in favor of H_1 if there is evidence at the $\alpha = 5\%$ significance level using a 2-sided test. Furthermore if H_0 is rejected in favor of H_1 and the overall LS mean is less for the lofexidine dose in comparison to placebo, then any lofexidine dose for which there is evidence of a difference will be declared superior to placebo in the treatment of opioid withdrawal in adult patients with opioid dependence. To account for multiplicity of statistical hypothesis testing of two lofexidine doses, statistical significance of the comparison of high dose lofexidine to placebo must be established, before significance of the comparison of low dose lofexidine to placebo can be claimed.

Justification

The primary efficacy endpoint has changed from the area under the curve (AUC) from Days 1 to 7 of the SOWS-Gossop scores to the overall (i.e., averaged over study Days 1 through 7) least squares (LS) means from a pattern mixture model based on log-transformed SOWS-Gossop scores from Days 1 through 7. The new endpoint stems from a revision of the pattern mixture model that incorporates comments on the modeling approach from the US Food and Drug Administration (FDA) in relation to patients who discontinue treatment.

Using the proposed pattern mixture model, the combined process of imputation followed by MMRM does not assume MAR and provides an unbiased estimate of the treatment effect that follows under the assumption that the mechanism by which data are missing not at random (MNAR) is that upon withdrawal from the study, the SOWS-Gossop trajectory of subjects randomized to lofexidine evolves as the trajectory of placebo subjects. Thus, by assigning an

Effective: 24-Dec-2014

Page 6 of 29

unfavorable placebo trajectory to patients who discontinue lofexidine treatment, the proposed model has addressed this concern. The nature of these changes is described in Change 7, following.

Change 7

Section 6.9.1 Principal Analysis

Amend to

A pattern-mixture approach⁵ will be used in assessing SOWS-Gossop from Days 1 to 7 inclusive using the mITT population.

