On days where a discontinuation visit is recorded on the same day as a scheduled visit, then the **scheduled visit** should be used be for analysis purposes and the discontinuation visit will be ignored. If a discontinuation visit is recorded on a study day where no scheduled visit is recorded, then it should be assigned to the **actual study day** the visit was recorded.

Justification

Effective: 22-Jan-2015

Page 5 of 11

To further clarify a set of rules for how to handle assessments recorded on the date of discontinuation instead of the scheduled study visit.

Change 6

Section 6.9.1 Principal Analysis

The following text in bold has been revised:

A pattern-mixture approach⁵ will be used in assessing SOWS-Gossop from Days 1 to 7 inclusive using the mITT population.

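### SAP Addendum 2 lets a discontinuation-visit SOWS-Gossop stand as that day's observed score without excluding scores taken after rescue opioids or other exclusionary drugs

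*SAP*

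**What the plan says.** **Scheduled score.** Protocol Table 1, footnote (e), places the Days 1-7 SOWS-Gossop "3.5 hours (±10 minutes) after the first dose of study medication followed by the other efficacy scales shortly thereafter".

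**Exit score.** Protocol 15.3.3 lists the SOWS-Gossop among the discontinuation "assessments and procedures as listed below after the last dose of study medication". The asterisked note to Table 1 adds that these are done whenever a subject leaves the study. No clock window is given.

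**Treatment after removal.** For subjects removed because of adverse events, Protocol 14.5.1 states: "This stabilization can include medically supervised opioid withdrawal (involving behavioral therapy, rescue opioid medications, and/or non-opioid pharmacotherapy"), or referral to a methadone or buprenorphine program. Under Protocol 14.6, if a subject needs other medication for intolerable nausea and emesis, "the subject will be discontinued from the study and given appropriate treatment according to the standard of care".

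**Assignment rule (Addendum 2, Change 5).** It has one filter: "On days where a discontinuation visit is recorded on the same day as a scheduled visit, then the" scheduled visit is used and the exit visit is ignored. For all other days the rule is: "If a discontinuation visit is recorded on a study day where no scheduled visit is recorded, then it should be assigned to the" day on which it took place.

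**Primary analysis (Addendum 1, Changes 6 and 7; Addendum 2, Change 6).** A pattern-mixture approach "will be used in assessing SOWS-Gossop from Days 1 to 7 inclusive using the mITT population". Only missing values are imputed. The stated missing-data mechanism is that "upon withdrawal from the study, the SOWS-Gossop trajectory of subjects randomized to lofexidine evolves as the trajectory of placebo subjects".

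**The concern.** A subject who leaves before the late-morning assessment has no scheduled score that day, so the exit score takes its place. If an opioid or other exclusionary drug was given first, the score may partly reflect that drug rather than the randomized treatment.

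The effect reaches beyond that one day. The monotone imputation for day t conditions on earlier scores, so a lowered exit score lowers the imputed days after it. In a lofexidine subject, the first value after withdrawal is then not the placebo-like course that the SAP assumes. In a placebo subject, the score joins the data from which missing days in the lofexidine arms are imputed. What is at stake is an uncontrolled shift in the primary contrast, of unknown sign, that no planned sensitivity analysis isolates.

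**Working it through.** **1. Reading the passages together.** The plan states no figure on this point, so there is none to reproduce. The textual check has three parts.

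- *Is any exit score excluded because of an intervening drug?* No. Change 5 filters only on whether a scheduled visit exists that day.
- *Is the primary endpoint exempt?* No. Change 5 sits under derived data and does not name the endpoint, but nothing carves it out.
- *Does another rule catch it?* No. The per-protocol exclusion for excluded medication (Addendum 1, Change 3) affects only a sensitivity analysis. The restriction to days on treatment (Addendum 1, Change 13) covers only concomitant-medication counts. The tipping-point increments apply to missing lofexidine visits, so an observed exit score is left as it is.

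**2. Size, on assumptions.** The documents give no dropout by arm, no rescue rate and no SD. Assumed values:

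- dropout d of 30-60% per arm, with exits on Days 2-5;
- share a of dropouts affected, 10-30% per arm;
- a score of 12 recorded as 3, so on the log_e(score+1) scale δ = ln 4 − ln 13 = −1.179;
- day-to-day correlation 0.75 and SD 0.7.

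Shift in the seven-day contrast (lofexidine minus placebo), exit day alone:

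Δ₁ = (a_L·d_L − a_P·d_P) × δ / 7

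Carry-over to later days decays roughly as 0.75^j. The effective number of affected days is 1 + 0.75 + … + 0.75^(7−exit day), which is 3.29, 3.05, 2.73 and 2.31 for exits on Days 2, 3, 4 and 5. The mean is 2.85, so Δ ≈ 2.85 × Δ₁.

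| Case | a_L·d_L | a_P·d_P | Δ₁ | Δ approx. |
|---|---|---|---|---|
| Placebo more affected | 0.10×0.30 = 0.03 | 0.30×0.60 = 0.18 | +0.025 | +0.07 |
| Lofexidine more affected | 0.30×0.60 = 0.18 | 0.10×0.60 = 0.06 | −0.020 | −0.06 |
| Equal dropout and equal share | equal | equal | 0 | 0 |

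This approximation ignores the change that contaminated placebo scores make to the imputation regression. A simulation on the same assumptions, with regressions fitted to placebo data and used for both arms, compared the present rule with setting affected scores to missing. It gave about −0.05 to +0.08, and close to zero when dropout and share were equal in the two arms.

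In terms of geometric mean (score+1), e^0.08 = 1.083 and e^(−0.05) = 0.951, or about 8% up and 5% down in the ratio.

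**3. Milder assumptions.** Take a score of 5 in place of 12 (δ = ln 6 − ln 13 = −0.773) and the same affected share in both arms.

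- Smallest case: dropout 40% placebo and 30% lofexidine, 25% affected, one day: (0.30 − 0.40) × 0.25 × (−0.773) / 7 = +0.003.
- Largest case: dropout 60% and 40%, 75% affected, three days: (0.40 − 0.60) × 0.75 × (−0.773) × 3 / 7 = +0.050.

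**The case against.** The strongest reply is that the harmful sequence is inferred. No passage says the exit SOWS-Gossop follows rescue. Table 1 ties it to exit, and Protocol 14.5.1 and 14.6 describe treatment of subjects already removed. This stands as to frequency. It does not close the gap, because neither document requires the score to come first or excludes it if it does not.

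The scale asks about the last 24 hours or since the last test (Protocol 15.4.1), so an exit score should also cover hours before rescue and on study drug. This stands too: a fall from 12 to 3 is a strong assumption, and a reader who takes a post-opioid score as measuring only the opioid goes further than the scale allows.

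The rule is also narrow, since it acts only on days without a scheduled score. That limits how many subjects are affected.

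Finally, keeping observed scores after discontinuation can be a deliberate choice. Setting placebo scores to missing imputes an untreated course, which raises the placebo mean relative to the present rule and so helps lofexidine. The second half stands and is why the present rule should still be reported. The first half fits poorly: Change 5 is justified only as clarifying visit handling, while the principal analysis states a different assumption about what follows withdrawal.

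**Conclusion.** The gap is real and should be closed. Change 5 admits exit scores taken after opioids or exclusionary drugs into the primary analysis as observed values. That conflicts with the assumption stated for lofexidine withdrawals and can contaminate the placebo reference data. On the assumptions above, the contrast moves by about −0.05 to +0.08 log units. The frequency is unknown.

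Three stronger readings are not supported:

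- *That the rule biases the trial toward no effect.* This needs more affected subjects on placebo, which the documents do not show. The reverse pattern favors lofexidine.
- *That it breaks the placebo-trajectory assumption in every arm.* That assumption is stated only for subjects randomized to lofexidine. In placebo the problem is the reference data.
- *That the bias is the fall in one arm's mean.* That fall is about 0.02 to 0.17 log units with 40-60% dropout and 10-50% of dropouts affected, but only the difference between arms biases the contrast.

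**What to change.** Add to SAP Section 6.2, before unblinding: using the concomitant-medication records, flag any Day 1-7 discontinuation-visit score dated on or after the date of an opioid, methadone, buprenorphine or other exclusionary drug given after the last study dose. Set flagged scores to missing so that the Section 6.9.1 imputation applies. Repeat the primary analysis under the present Change 5 rule as a sensitivity analysis, and report the number of flagged scores by arm.

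Protocol 14.6 already requires medication dates, so no new form field is needed. An arbitrary limit on hours since the last dose is not needed either. The cost is a few sentences, one derivation and one extra model run. A few observed scores become imputed, including some where the score in fact came before the drug on the same date. Care of subjects does not change.
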